### ***Statistical Analysis***

Based on a pilot trial showing a pronounced reduction (30 day relative risk reduction 78%) in POAF after injecting BoNTA into the epicardial fat pads, we anticipated a significant reduction in the risk for POAF with epicardial BoNTA injection in our cohort. Our study sought to include valve surgery patients, which would result in a higher-risk population for POAF. Based upon a two-tailed alpha of 0.05, an estimated POAF incidence of 40% in the control group, and a total sample size of 130 (n=65 in each arm), we prospectively determined 80% power to detect a 40% difference in relative risk (corresponding to a hazard ratio of 0.4) between treatment groups for the primary outcome.

Analyses were based on the intention-to-treat principle in all patients who received epicardial injection (modified intention-to-treat analysis). Patient characteristics were summarized by standard descriptive statistics and were compared between groups using t-tests, Wilcoxon rank sum tests, Chi-square tests, or Fisher exact tests as appropriate. The Kaplan-Meier method was used to construct non-parametric estimates of the distribution of time to first POAF event. Adjustment of treatment effect for baseline factors previously found associated with POAF outcome was accomplished using Cox proportional hazards modeling. The proportional hazards assumption was confirmed via log-log plots, plots of Schoenfeld residuals by time, and testing of a group-time interaction in the model. Secondary analyses were conducted via parametric and non-parametric assessments as appropriate.

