Secondary analysis of incidence of POAF was conducted via univariable and adjusted logistic regression with the same baseline characteristics as in the primary outcome model. Heterogeneity of treatment effect was explored in patient subgroups defined by surgery type, POAF risk as assessed by the Multicenter Study of Perioperative Ischemia (McSPI) AFRisk index, preoperative angiotensin converting enzyme inhibitor (ACEi) use, beta-blocker use, diabetes, and congestive heart failure. We studied differences in ICU and hospital LOS via Wilcoxon rank sum tests. In order to characterize severity of POAF between groups, we explored group differences among patients who developed POAF in duration of first POAF, initial ventricular rate, total POAF duration (cumulative duration of all in-hospital POAF), and total POAF burden (percent of postoperative hospital LOS spent in AF) via Wilcoxon rank sum tests. We compared the incidence of recurrent POAF, hemodynamically significant POAF, two or greater days of POAF, and need for treatment for AF via Chi-Square or Fisher exact tests. We investigated differences in the incidence of safety endpoints via Chi-Square or Fisher exact tests, and used a Wilcoxon rank sum test to explore differences in duration of postoperative mechanical ventilation.

Because multiple comparisons of secondary outcomes were performed without post-hoc adjustment of the significance level, these outcomes should be interpreted as

exploratory. All comparisons were 2-tailed and significance was set at  $p<0.05$ . Analyses were performed using SAS version 9.4 (SAS Inc., Cary, NC). A data safety monitoring board consisting of a cardiothoracic surgeon, cardiothoracic anesthesiologist, cardiac electrophysiologist, and biostatistician examined blinded, aggregate adverse event data at 10%, 25%, and 50% accrual in order to ensure adequate safety of the study.

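### ICU stay, hospital stay and ventilation time are tested only without covariates; the test is valid, but adding an adjusted analysis could gain some precision at little cost

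*Combined protocol and SAP*

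**What the plan says.** All the relevant text is in the Statistical Analysis section of the combined protocol and SAP.

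- ICU and hospital stay: "We studied differences in ICU and hospital LOS via Wilcoxon rank sum tests".
- Ventilation time, among the safety analyses: the plan "used a Wilcoxon rank sum test to explore differences in duration of postoperative mechanical ventilation".
- Time to POAF (primary): "Adjustment of treatment effect for baseline factors previously found associated with POAF outcome was accomplished using Cox proportional hazards modeling".
- Incidence of POAF (secondary): "univariable and adjusted logistic regression with the same baseline characteristics as in the primary outcome model".

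The baseline factors in the two POAF models are not listed. Surgery type, the AFRisk index, diabetes and congestive heart failure appear by name as subgroup factors, so they are recorded. A general sentence leaves secondary analyses to parametric or non-parametric methods as suitable, and adds no adjustment. No adjusted, stratified or regression analysis of stay or ventilation time is described anywhere. The same section labels the secondary outcomes exploratory, because no multiplicity adjustment is made.

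**The concern.** The plan treats baseline risk as worth modelling for POAF and then leaves it out for the three durations measured in all patients. The cohort mixes CABG, valve and combined surgery at two hospitals. Randomization and Masking describes 1:1 allocation in mixed blocks and mentions no stratification. If surgery type or comorbidity predicts stay or ventilation time, that variation stays in the error term of a plain rank test.

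The stake is precision. Ventilation time is the only continuous measure listed among the safety end points, and a non-significant safety comparison can be read as reassurance. For these durations the plan names only a test, with no effect estimate or confidence interval. A reader could not tell a small difference from an imprecise one.

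**Working it through.** **1. The plan's own power figure.** Inputs: "Based upon a two-tailed alpha of 0.05, an estimated POAF incidence of 40% in the control group", "a total sample size of 130 (n=65 in each arm") and "80% power to detect a 40% difference in relative risk (corresponding to a hazard ratio of 0.4").

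- Treated-arm incidence under a hazard ratio of 0.4: 1 − 0.6^0.4 = 0.185.
- Expected events: 65 × (0.40 + 0.185) = 38.0.
- Schoenfeld power: Φ(√(38.0/4) × |ln 0.4| − 1.96) = Φ(0.86) = 80.6%.

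The stated 80% reproduces from the hazard ratio, but it covers the primary outcome only. The documents give no SD, target difference or power for stay or ventilation time, so the rest of the working uses assumed values.

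**2. Outcomes side by side.**

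| Outcome | Planned analysis | Baseline covariates |
|---|---|---|
| Time to POAF | Cox model | Yes, not listed |
| POAF incidence | Logistic, univariable and adjusted | Yes, same set |
| ICU stay, hospital stay | Wilcoxon | None |
| Ventilation time | Wilcoxon | None |

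**3. Chance imbalance.** For a binary factor with assumed prevalence p, the SE of the difference between arms is √(2p(1−p)/65).

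- p = 0.3: SE 0.080. A gap of 10 points or more has z = 1.24, probability about 21%.
- p = 0.5: SE 0.088, z = 1.14, probability about 25%.

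Such gaps are common at this size. The Wilcoxon null distribution already allows for them, so they cost precision and not validity.

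**4. Approximate gain from adjustment.** The Wilcoxon efficiency relative to the t-test is 3/π = 0.955 for normal data. The shift detectable with 80% power at 65 per arm is (1.96 + 0.842) × √(2/(65 × 0.955)) = 0.503 SD. Adjustment multiplies the SE by √(1−R²), so power becomes Φ(2.802/√(1−R²) − 1.96).

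| Assumed R² | SE ratio | Detectable shift (SD) | Power |
|---|---|---|---|
| 0 | 1.000 | 0.503 | 80% |
| 0.05 | 0.975 | 0.490 | 82% |
| 0.10 | 0.949 | 0.477 | 84% |
| 0.20 | 0.894 | 0.450 | 88% |
| 0.30 | 0.837 | 0.421 | 92% |

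**5. Simulation, 65 per arm, skewed (log-normal) outcome.** The approximation ignores the cost of estimating covariate effects, so it was checked in two settings, each with five covariates and 4,000 trials per power figure.

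- A: shift of 0.503 SD, adjusted analysis on normal scores of the ranks.
- B: log SD 0.40 and an 18% shorter stay, analysed by rank analysis of covariance. The standardized shift is −ln(0.82)/0.40 = 0.496, and the formula gives Wilcoxon power Φ(0.496/0.1795 − 1.96) = 79%.

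The last column repeats scenario B, in whole percentages.

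| Assumed R² | A: Wilcoxon → adjusted | B: Wilcoxon → adjusted | B repeated |
|---|---|---|---|
| 0 | 79.7 → 79.4 | 79.0 → 77.4 | 80 → 78 |
| 0.05 | 80.5 → 82.1 | 78.0 → 78.5 | 79 → 80 |
| 0.10 | 78.7 → 83.0 | 78.9 → 80.5 | 79 → 81 |
| 0.20 | 79.4 → 87.7 | 78.0 → 84.6 | 78 → 83 |
| 0.30 | 79.0 → 91.2 | 77.9 → 89.0 | 78 → 89 |

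The Monte Carlo SE of a single power figure from 4,000 trials is √(0.8 × 0.2/4000) = 0.6 points, so differences of a point or so between columns mean little. In A, type I error was 4.2–5.3% for Wilcoxon and 4.8–5.5% adjusted. In B it was 5.1–5.4% adjusted.

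A weaker assumed effect gives small gains at low R². With a 10% shorter stay and one covariate (3,000 trials), power went from 30.1% to 31.7% at R² 0.05 and from 30.1% to 32.2% at 0.10.

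**The case against.** The strongest reply is that nothing is wrong with the planned test. It is valid under 1:1 randomization, controls type I error and suits skewed durations. That stands in full.

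A reader might infer that the plan discards precision it certainly had, or that covariates are its only cheap source of power. The documents support neither reading. The Cox factors were chosen for association with POAF, and nothing says that they, or the subgroup variables, predict stay or ventilation time. No R² is given. At R² 0.10 or below the gain is a few points at most, and at zero there is a slight loss. The simulations also model a generic skewed duration. Ventilation time was not modelled separately.

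A reader might also infer that the Wilcoxon tests should be replaced. That does not follow either: they are sound, the outcomes are exploratory, and the document is written in the past tense, so a substitution could come after the results were known.

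What survives is narrower. The factors are recorded, an adjusted analysis costs almost nothing and keeps type I error near 5%, and an estimate with an interval is useful whatever the covariates explain.

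**Conclusion.** The point holds as a modest efficiency and reporting improvement for exploratory outcomes. The primary analysis, the sample size and the validity of the planned tests are unaffected.

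At 65 per arm, with an assumed effect giving about 78% unadjusted power, adjustment changes power by:

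- a loss of up to about 2 points if the covariates explain nothing;
- a gain of about 1 to 4 points at R² 0.05 to 0.10;
- a gain of about 5 to 12 points at R² 0.20 to 0.30.

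The R² values, the effect and the log-normal shape are assumptions. The 65 per arm is the planned number, and the modified intention-to-treat set may be slightly smaller.

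**What to change.** Keep the three Wilcoxon tests. Add one covariate-adjusted analysis for each of ICU stay, hospital stay and ventilation time.

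- **Method:** rank analysis of covariance (regress the ranks on the covariates and compare mean residual ranks by arm). Proportional-odds regression is a model-based alternative. It is not interchangeable, since it estimates a conditional odds ratio and adds the proportional-odds assumption.
- **Covariates:** a short list named in the SAP, chosen because the factors are expected to predict these durations and without reference to results by arm. Surgery type, the AFRisk index, congestive heart failure and diabetes are candidates. Pointing to the Cox model's factors is not enough while those remain unlisted.
- **Reporting:** an effect estimate with its 95% confidence interval for each duration. Under rank analysis of covariance, the adjusted difference in mean ranks divided by the number analysed estimates the probability of a longer duration on active treatment, minus one half.
- **Timing:** label the analysis post hoc if results are already known.

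The cost is a paragraph of SAP text and a few lines of code, with no new data. The downside is the slight loss of power if the chosen factors are not prognostic.

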#### **Outcomes**

The primary end point of this study was time to  $>30$  seconds of in-hospital POAF as assessed by continuous telemetry during the postoperative hospitalization. Pre-specified secondary end points included the incidence of POAF, and among those developing POAF the duration of first POAF episode, in-hospital burden of POAF (percent of postoperative hospitalization spent in AF), proportion of recurrent (greater than one episode lasting  $>30$ s) or prolonged (two days or greater in duration) POAF, and need for POAF treatment (medications administered for rate control, rhythm control, or electrical cardioversions for POAF). Additionally, the ICU and hospital LOS were compared between groups. As an exploratory analysis, we also examined the incidence of

hemodynamically significant new-onset POAF, resulting in rapid ventricular response (heart rate > 100 BPM) and hypotension (systolic blood pressure < 100 mmHg).

Safety end points included the incidence of any adverse event or postoperative complication, the incidence of adverse events prolonging LOS, and postoperative mortality. Additionally, duration of postoperative mechanical ventilation and the incidence of reintubation were compared between groups.

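### POAF duration and burden are tested only in patients who developed POAF, the event treatment is meant to prevent, and the denominator for the related binary outcomes is not fixed

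*Combined protocol and SAP*

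**What the plan says.** All references are to the Combined protocol and SAP.

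- **Outcomes** defines the secondary end points "among those developing POAF the duration of first POAF episode, in-hospital burden of POAF". The same list goes on to "proportion of recurrent (greater than one episode lasting" 30 seconds) or prolonged POAF, and ends with "need for POAF treatment (medications administered for rate control, rhythm control, or electrical cardioversions for POAF".
- **Statistical Analysis**, secondary analyses, repeats the restriction for the continuous measures: "we explored group differences among patients who developed POAF in duration of first POAF, initial ventricular rate, total POAF duration". It adds total burden, and all are tested by Wilcoxon rank sum.
- The next sentence covers the binary outcomes without that restriction: "We compared the incidence of recurrent POAF, hemodynamically significant POAF, two or greater days of POAF", and "need for treatment for AF via Chi-Square or Fisher exact tests". No denominator is given.
- The general analysis population, set earlier in the same section, is wider: "Analyses were based on the intention-to-treat principle in all patients who received epicardial injection".
- Secondary outcomes are labelled exploratory because "multiple comparisons of secondary outcomes were performed without post-hoc adjustment of the significance level".

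No analysis of total POAF duration or burden in all injected patients is described.

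**The concern.** The trial expects the injection to lower the risk of POAF. Restricting a between-arm test to patients with POAF therefore conditions on something treatment changes. The two POAF groups need not be alike at baseline. If treatment removes the easily prevented, short episodes, the active arm keeps the stubborn ones, and its median duration rises although no episode has become longer. If it removes the long ones, the error runs the other way.

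The restriction is unavoidable for first-episode duration and initial ventricular rate, which do not exist without POAF. It is avoidable for total duration and burden, which equal 0 in a patient who never fibrillates.

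The second problem concerns the binary outcomes. Under Outcomes they read as conditional on POAF. Under Statistical Analysis they are called incidences, and the default population is everyone injected. Two programmers could build different tables from the same text.

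A POAF-only test could thus be reported as harm on severity when treatment only prevents AF. A real reduction in, say, patients needing AF treatment could also vanish or appear with the denominator. The exploratory label warns about multiplicity, not selection.

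**Working it through.** **Inputs (Statistical Analysis).** 65 patients per arm; control POAF incidence 40%; two-sided alpha 0.05; an effect given both as a 40% relative difference and as a hazard ratio of 0.4. These two effects imply different active-arm incidences, so both are carried through.

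**Plan's own figure.** At HR 0.4, active incidence = 1 − 0.6^0.4 = 18.5%. Events = 65 × (0.400 + 0.185) = 38.0. Schoenfeld power = Φ(½ × √38.0 × |ln 0.4| − 1.96) = Φ(0.86) = 80.6%, which matches the stated 80%. No power is stated for the POAF-only tests.

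**Size of the subset.**
- HR 0.4: 65 × 0.40 = 26 control and 65 × 0.185 = 12 active. Excluded: (130 − 38)/130 = 71%.
- 40% relative reduction: active incidence 0.40 × 0.6 = 24%, so 26 control and 65 × 0.24 = 15.6, about 16, active. Excluded: (130 − 42)/130 = 68%.

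**Selection by arithmetic.** Assume 20% of control cases are prolonged (26 × 0.20 = 5.2) and treatment prevents only shorter cases.
- Among POAF cases: 20% v 5.2/12.0 = 43% (HR 0.4), or 20% v 5.2/15.6 = 33% (40% reduction).
- Among all patients: 5.2/65 = 8% in both arms.

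**Selection by simulation.** Each patient has a latent POAF propensity and a log-duration with correlation ρ. Thresholds on propensity give the incidences above. Treatment has no effect on duration. There were 6,000 trials per cell, with a two-sided Wilcoxon test at 0.05.

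| ρ | POAF-only, significantly longer on active (18.5% / 24%) | All patients, significantly in favour of active (18.5% / 24%) |
|---|---|---|
| 0 | 2.2% / 2.2% | 76% / 49% |
| 0.3 | 5.4% / 4.7% | 74% / 45% |
| 0.5 | 10.6% / 7.4% | 72% / 44% |
| 0.7 | 19.3% / 12.0% | 70% / 40% |
| 1.0 | 78.4% / 57.5% | 57% / 31% |

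The nominal rate in the first results column is 2.5%. The all-patient test was significant against active in at most 0.03% of trials. A repeat run agreed within simulation error (for example 20.3% / 12.5% at ρ = 0.7). In a separate simulation at correlation 0.6, median duration among POAF cases was 37% longer on active at HR 0.4 and 24% longer at a 40% reduction, with no drug effect on any episode. When the prevented cases were a random subset, two-sided rejection stayed at about 5%.

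**Denominator (Fisher exact; assumes about 80% of POAF cases are treated in both arms).**

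| Active cases | POAF-only | All patients |
|---|---|---|
| 12 | 21/26 v 10/12 (81% v 83%), p = 1.0 | 21/65 v 10/65 (32% v 15%), p = 0.039 |
| 16 | 21/26 v 13/16 (81% v 81%), p = 1.0 | 21/65 v 13/65 (32% v 20%), p = 0.16 |

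**Prolonged POAF, POAF-only.** 10/26 v 10/12 gives p = 0.015 against treatment, but that is an extreme split. 10/26 v 8/12 gives p = 0.16, and 10/26 v 10/16 gives p = 0.20.

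**The case against.** The POAF-only tests serve a stated aim, to describe how severe POAF is, and severity exists only in those who have it. Time to POAF and POAF incidence already compare the arms without the restriction. The bias needs a link between propensity and duration that the documents do not supply: at correlation 0 there is none, at 0.3 it is small, and the figures at 1.0 describe a deterministic link. If incidence does not differ between arms, this model gives no bias. In the modelled direction it works against the drug, so it would not create a false claim of benefit. The all-patient test largely repeats the incidence result, and its near-zero false-harm rate is almost automatic when active treatment truly lowers incidence. The p = 0.039 example also echoes incidence, since 26/65 v 12/65 alone gives p = 0.012. Finally, the outcomes are secondary and exploratory, and the Outcomes list reads most naturally as conditional throughout.

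Most of this stands as a limit on weight. The size of the bias is unknown, the POAF-only summaries should stay, and the all-patient result must not be read as severity. It does not remove the problem. The plan gives a between-arm significance test in a post-randomisation subset as the only analysis of duration and burden, with no caveat about selection. The direction is not guaranteed either: with a negative correlation the simulated rates mirror exactly and would favour the drug. The conditional reading of the list is plausible, but the later use of incidence and the all-injected default leave it open.

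**Conclusion.** The concern holds on both counts. The restriction is explicit in both sections, and the plan describes no all-patient analysis of total duration or burden. On the design assumptions, the POAF-only tests use 38 to 42 of the 130 patients. Their false-harm rate ranges from nominal (no correlation) to about 5% at correlation 0.3, 7-11% at 0.5 and 12-19% at 0.7. Those rates assume that treatment prevents POAF in the least susceptible patients and leaves duration unchanged; the documents fix neither the direction nor the size. For the binary outcomes the denominator can change the conclusion in one plausible case and not in another; this part is a gap in wording.

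The primary end point, POAF incidence, length of stay and safety are untouched. The change is worth making because it is cheap, but it does not threaten the trial's main result.

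**What to change.** 1. Compare total POAF duration and burden between arms in all injected patients by Wilcoxon test, scoring no POAF as 0. Describe the result as total AF load, not severity. State how in-hospital deaths and short monitored stays are handled.
2. State that recurrent POAF, POAF of two days or more and need for POAF treatment use all injected patients as denominator (no POAF counts as no), and bring Outcomes into line with Statistical Analysis. State the denominator for haemodynamically significant POAF too, which shares the sentence.
3. Keep the POAF-only results, including first-episode duration and initial ventricular rate, as descriptive summaries marked as not protected by randomisation.

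**Cost.** No new data are needed, only a different denominator and clearer wording. The text is in the past tense, so if the analyses are complete this should be labelled as an added re-analysis. The real drawback is that the all-patient test mixes incidence with duration: with no duration effect it still favoured active in 57-76% of simulated trials at 18.5% incidence and 31-49% at 24%. The POAF-only summary is therefore needed beside it.

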#### **Procedures**

The attending cardiac surgeon performed injections immediately after initiation of cardiopulmonary bypass, prior to the primary surgical procedure. Study solution (1mL consisting of 50 units onabotulinumtoxinA or 1mL placebo) was injected using a 27g needle under direct vision into all five epicardial fat pads, including the anterior fat pad, and the fat pads associated with each pulmonary vein. The remainder of perioperative care was managed according to the primary team.

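### First-episode POAF duration and two-day POAF are tested as if every episode were seen to its end, although observation stops at discharge

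*Combined protocol and SAP*

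**What the plan says.** The Outcomes section ascertains postoperative AF (POAF) "as assessed by continuous telemetry during the postoperative hospitalization". No rhythm monitoring after discharge is described.

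Among the secondary endpoints, that section lists "among those developing POAF the duration of first POAF episode" and POAF that is "prolonged (two days or greater in duration". The Statistical Analysis section says "we explored group differences among patients who developed POAF in duration of first POAF", and does so by Wilcoxon rank sum test. It compares "two or greater days of POAF" by chi-square or Fisher's exact test. Kaplan-Meier and Cox methods are named for time to first POAF only.

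No section says how an episode that is still running at discharge or death is to be scored. Under Procedures, "The remainder of perioperative care was managed according to the primary team". The treatments counted under Outcomes are "medications administered for rate control, rhythm control, or electrical cardioversions for POAF". The plan describes its secondary outcomes as exploratory, on the ground that no multiplicity adjustment is made.

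**The concern.** The observed length of an episode cannot exceed the time from its onset to discharge. The planned tests treat that observed length as the full one. Discharge in AF is foreseeable, because care is left to the treating team and rate control, which need not restore sinus rhythm, is among the listed treatments.

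Suppose AF starts 10 h before discharge and the patient goes home in AF. The recorded duration is 10 h, which ranks as milder than a 12 h episode that ended in hospital. That patient also cannot meet the two-day criterion, whatever happens later.

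The truncation need not be equal between arms. The primary endpoint is time to onset, so a treatment that delays onset also narrows the window in which its severity endpoints are seen. Length of stay is itself compared between arms and acts on the same window. Part of a difference in AF severity could therefore come from timing alone.

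**Working it through.** **1. The plan's own figure.** The documents give no power or precision for these endpoints, only 80% power for the primary outcome (130 patients, 40% control incidence, hazard ratio 0.4). It reproduces:
- Treated incidence: 1 − 0.6^0.4 = 18.5%.
- Expected POAF patients: 65 × 0.40 = 26 and 65 × 0.185 = 12, together 38.
- Schoenfeld power: Φ(√(38/4) × |ln 0.4| − 1.96) = Φ(2.82 − 1.96) = 80.6%.

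The severity comparisons thus rest on about 26 against 12 patients.

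**2. Model of the truncation.** Observed duration = min(true duration, discharge − onset), with the same true durations in both arms. The following inputs are assumptions, not taken from the documents:
- onset lognormal, median 2.3 days, log-SD 0.5;
- stay lognormal, median 5, 6 or 7 days, log-SD 0.2, independent of AF;
- duration lognormal with 25.7% lasting 48 h or more (log-SD varied from 1.0 to 1.5, with little effect on the observed shares).

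**3. Two ways in which onset may differ between arms.**
- *Proportional hazards with the plan's figures.* Control cumulative incidence is 0.40 × G(t), where G is the assumed onset distribution. Treated incidence is 1 − (1 − 0.40 × G(t))^0.4. Median onset among treated cases solves 1 − (1 − 0.40 × G)^0.4 = 0.185/2, so G = 0.538 and onset is 2.41 days. The shift from 2.30 days is about 2.7 h.
- *A pure delay of one day.* The documents do not predict this. It serves as a larger case.

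Observed share with 48 h or more (true share 25.7% in both arms):

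| Median stay | Control | Hazard ratio 0.4 | 1-day delay |
|---|---|---|---|
| 5 days | 18.4% | 17.8% | 12.4% |
| 6 days | 21.9% | 21.5% | 18.0% |
| 7 days | 23.7% | 23.4% | 21.6% |

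Relative to control, the spurious reduction under the hazard ratio is 1 − 17.8/18.4 = 3%, 1 − 21.5/21.9 = 2% and 1 − 23.4/23.7 = 1%. Under the one-day delay it is 1 − 12.4/18.4 = 33%, 1 − 18.0/21.9 = 18% and 1 − 21.6/23.7 = 9%. The control arm is itself understated: 18.4-23.7% against 25.7%.

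**4. A second set of assumptions.** Onset median 2.5 days (log-SD 0.4), stay median 6 days (log-SD 0.3), duration median 1.0 day (log-SD 1.5), true two-day share 32%.
- No discharge held until AF ends: the observed share is 25.9% with no delay and 20.9% with a one-day delay, a relative drop of 19%.
- Half of those still in AF held until it ends: 29.0% and 26.6%, a relative drop of 8%.

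**5. Effect on the tests.** With 26 against 12 POAF patients, the inputs of step 4 and none held, the false-positive rate goes from 4.2% to 5.7% for Wilcoxon and stays at 3.0% for Fisher under a one-day delay.

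**6. Check of the remedy.** In the model of step 2, the Kaplan-Meier estimate at 48 h, censored at discharge, returned 25.7% to within simulation error. The plain count gave 12-24%. This recovery depends on the model's assumption that discharge is unrelated to how long AF lasts.

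**The case against.** The strongest reply is that the effect is small where it can be tied to the plan. The plan anticipates fewer POAF cases, not a uniform delay, and its hazard ratio moves onset among cases by under three hours. The false-positive rate barely changes, the outcomes are declared exploratory, and the primary endpoint is not involved. All of this stands, and it limits the weight of the point. The exploratory label, however, answers multiplicity and does not remove a bias in the estimate.

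Three stronger readings are tempting, and the documents do not support them.
- A reader might infer that everyone sent home in AF is scored as short and not prolonged. The documents state no scoring rule, and AF that began at least two days before discharge would still count. Under the assumptions of step 4 and its variants (stay median 6 or 7 days, duration median 0.5 or 1.0 day), 28-48% of those discharged in AF score under two days with no delay, and 44-66% with a one-day delay.
- A reader might take 9-33% as the expected bias. It requires an assumed one-day delay and a stay unrelated to AF.
- A reader might conclude that the two sections define different endpoints, so that brief AF on two separate days would qualify under one of them. That is strained: both phrases carry the same reference, and neither ties the two days to a single episode. What is missing from both is whether the time is continuous or cumulative.

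The in-hospital limit is explicit for the telemetry, total duration and burden. For first-episode duration and two-day POAF it is inferred, because no other data source is described.

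**Conclusion.** The point holds in a limited form. Episodes still running at discharge or death are analysed as complete, which understates duration and the two-day share in both arms, and more so in an arm with later onset or shorter stay. How much cannot be determined, since neither the number discharged in AF nor the dependence of discharge on rhythm is given. Under the assumptions shown, the distortion between arms runs from about 1-3% relative (the plan's incidence and hazard ratio) to 9-33% (a pure one-day delay), and is less where discharge waits for AF to end. At this sample size the harm is a biased estimate more than a false claim of significance. The point is worth correcting because the remedy needs only a change in analysis.

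**What to change.** 1. Analyse first-episode duration as time to AF termination, censored at discharge or death if AF is ongoing, using Kaplan-Meier with a log-rank or Gehan-Wilcoxon test.
2. Take the two-day proportion from that Kaplan-Meier curve at 48 h. This fits a definition based on one continuous first episode. If cumulative AF is meant, the first-episode curve does not give it, and the bounds in item 3 have to carry the result.
3. Report the number in AF at discharge by arm. Bound the two-day count by scoring patients censored before 48 h first as not prolonged, then as prolonged. Do not make AF at discharge part of the main definition: with a 5-day stay and a one-day delay, that moves the share from about 31% to about 38% against a true 26%, so the bias is reversed, not removed.
4. Use one wording in Outcomes and Statistical Analysis that says whether two days means one continuous episode or cumulative AF.

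The cost is analysis and wording. Rhythm at discharge should already be on the telemetry record. The small downside is that censoring assumes discharge is unrelated to AF resolution, which is doubtful. The two bounds show how far the two-day result depends on that. Restricting the comparison to patients who developed POAF is a separate post-randomisation limitation, which these changes do not remove.
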